1 INTRODUCTION

Prostate cancer (PCa) is the most common cancer, and the second most common cause of cancer mortality amongst men in the United Kingdom with over 55,000 new patients diagnosed each year(1) . Multi-parametric magnetic resonance imaging (mpMRI) of the prostate has become an established tool for diagnosing PCa, resulting in an image targeted approach to biopsy (2). Diagnosed early, localized PCa can usually be cured with radical treatment such as surgery (radical prostatectomy) or radical radiotherapy(3). Despite the advancements in technique through the adoption of robotic-assisted surgery, there are still significant side effects that persist after radical prostatectomy. These include impairment in sexual function and urinary incontinence (4). These side effects carry a burden on PCa patients and have an impact on their wellbeing and quality of life. Poor sexual function is reported by most PCa patients (5). Every year, around 8,000 patients undergo radical prostatectomy in the National Health Service (NHS) of England. These factors contribute to a decline in psychosexual well-being and overall quality of life. If the nerves and blood vessels that surround the prostate are left intact during surgery (neurovascular bundle sparing), the risk of developing these side effects decreases. The recovery of erectile function (EF) after neurovascular bundle (NVB) sparing surgeries varies and is often unpredictable. The treatment options for erectile dysfunction (ED) after radical prostatectomy involve a systematic progression from medical interventions, such as medications, to intracavernosal injections, and ultimately to invasive treatments, such as the use of a penile prosthesis. The proportion of men who do not recover erections after NVB sparing surgery remains unclear.

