For the assessment, the surgeons will use a standardized framework to annotate the videos, employing key performance indicators aligned with the domains of the PACE tool, which will be modified to suit NVB assessment. Each NVB (e.g., two assessments for patients undergoing bilateral NVB sparing) will be evaluated using a Likert scale for each domain.

Relevant data points, such as the time taken for specific tasks, error rates, and adherence to the surgical protocol, will be manually extracted from the annotated videos.

3.5 Assessment of functional outcomes:

Patient reported outcomes of EF and urinary continence:

Evaluation of outcomes will be carried out using validated questionnaires. EF will be assessed using an ED screening tool, IIEF-EFD and EPIC-26. Urinary continence will be assessed using the EPIC-26 continence domain.

Participants will receive the questionnaires prior to surgery (baseline), week 6, month 6, 12 and 24. These time points correspond to the normal appointment schedules provided to patients under the post-RARP penile rehabilitation.

Participants will fill in the form on paper or electronically and this will be transferred to the database by the research clinical fellow. Data protection measures are outlined in section 11.

We will use RedCap platform to offer patients a chance to complete the questionnaires through an electronic platform either via email or smartphone.

3.6 Controlling surgical confounders:

3.6.1 Sources of confounders:

The confounders of EF recovery are categorized into three categories: pre-surgical, surgical, and post-surgical. Comorbidities and baseline erectile functions are pre-surgical confounders. The quality of bilateral NVB sparing and intraoperative surgical complications are surgical confounders. The patient's overall well-being, post-surgical complications, and penile rehabilitation are all post-surgical concerns. Further to these patients can develop metabolic conditions (during their follow-up) contributing or exacerbating their ED.

3.6.2 Management of confounders:

To control the pre-surgical confounders the study is focusing on men with no pre-existing ED and no established vascular disease that increase the likelihood of ED (IHD, PVD, CVD)

The surgical confounders will be adjusted for by limiting the surgeons in the study and measuring the quality of the NVB sparing and intraoperative complications.

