The post-surgical confounders will be balanced by administering a standardized, proven post-surgical penile rehabilitation protocol that is used by UCLH Urology. The protocol is provided is described in 1.2.5.

The post-surgical complications will be captured during follow-ups and the overall well-being will be captured through the validated tools administered. Appropriate statistical tests will be applied to adjust for these confounders. Patients who have ED will be investigated with routine blood tests to screen for metabolic causes of ED and will be accounted for in ad-hoc data analysis.

Further details of statistical analysis and methods employed to adjust for confounders are provided in the data analysis section.

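### Section 3.6 commits to adjusting erectile function for post-operative well-being, which the protocol's own account places downstream of erectile function and so is not a confounder

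*Protocol*

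**What the plan says.** Section 3.6.1 of the protocol opens with "The confounders of EF recovery are categorized into three categories: pre-surgical, surgical, and post-surgical". It fills the third category as follows: "The patient's overall well-being, post-surgical complications, and penile rehabilitation are all post-surgical concerns".

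Section 3.6.2 explains how that category will be handled. Rehabilitation is standardised and complications are recorded at follow-up. On well-being and adjustment it says that "the overall well-being will be captured through the validated tools administered. Appropriate statistical tests will be applied to adjust for these confounders". The section then sends the reader to the data analysis section for the methods of adjustment.

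On the tools, section 3.5 says "EF will be assessed using an ED screening tool, IIEF-EFD and EPIC-26", with EPIC-26 also covering continence. Questionnaires are given at baseline, week 6 and months 6, 12 and 24. Table 1 schedules only IIEF-EFD and EPIC-26. No instrument is identified as the measure of overall well-being.

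On direction, the Introduction says of impaired sexual function and incontinence that they "have an impact on their wellbeing and quality of life". The Lay Summary (section 1.1) says the same of sexual side effects, and names quality of life as something on which the effect of preserving the arteries is to be assessed.

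Section 7 plans regressions of 12-month EF on imaging parameters, video ratings and baseline EF. It does not mention well-being.

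**The concern.** A confounder of the APA-EF association must influence, or share a cause with, both APA status and EF. Well-being reported after the operation comes too late to influence whether an APA exists, whether it was preserved, or how well the neurovascular bundle (NVB) was spared. By the protocol's own account it is at least partly a result of how EF recovers.

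Conditioning on a variable that EF itself drives takes out part of the difference in EF that the analysis is looking for. The analyses at stake are the association of arterial categories with EF recovery (section 3.3) and the regressions of 12-month EF on imaging parameters and video ratings (section 7). If the rule in 3.6.2 were followed, a real association would tend to look weaker than it is, and the same rule could be carried into the full-scale study that this one is meant to inform.

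**Working it through.** The protocol gives no figure to reproduce on this point: no effect size, no correlation between well-being and EF, and no formula behind the target of 20-40 patients. The check is therefore a reading of timing and direction, followed by an illustration on stated assumptions.

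**1. Timing.** APA presence is read from the preoperative mpMRI (section 3.3). Preservation and NVB-sparing quality are settled during the operation (section 3.4). Section 3.6.1 puts well-being in the post-surgical category. A later variable cannot cause an earlier one, so the arrow from well-being to exposure that confounding would need is absent.

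**2. Direction.** The Introduction and the Lay Summary both run from sexual side effects to well-being. Section 3.6 instead treats well-being as a nuisance factor in EF recovery. These passages do not agree on the role of the variable.

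**3. Effect of adjusting, in the simplest case.** Assume that well-being W is purely a consequence of the EF score Y being modelled, and let X be APA status:

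- Y = bX + e, with var(e) = 1
- W = gY + u, with var(u) = 1
- partial correlation of W and Y given X: r = g / √(1 + g²), so 1 − r² = 1 / (1 + g²)
- regressing Y on X and W gives E[Y | X, W] = (bX + gW) / (1 + g²), so the coefficient of X is b / (1 + g²) = b(1 − r²)

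The documents give neither r nor b. Taking r from 0.3 to 0.7 and b = 0.5 SD as assumptions:

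| Assumed r | 1 − r² | 0.5 × (1 − r²) | Simulated coefficient, adjusted |
|---|---|---|---|
| 0.3 | 1 − 0.09 = 0.91 | 0.455 | 0.45 |
| 0.5 | 1 − 0.25 = 0.75 | 0.375 | 0.37 |
| 0.7 | 1 − 0.49 = 0.51 | 0.255 | 0.26 |

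The simulation used 400,000 records, with APA prevalence set at the 38.2% cited in section 1.2.4. Without W in the model it returned 0.50 in each case.

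**4. Sensitivity to the causal picture.**

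- With an added common cause of well-being and EF, adjustment still shrank the coefficient: 0.50 to 0.44, and 0.51 to 0.39, in two settings.
- If well-being only influences EF, is not influenced by it and is unrelated to APA status, adjustment does no harm (0.50 with and without W). In that case well-being is still not a confounder, because it is unrelated to the exposure.

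**The case against.** The strongest reply is that the specified models never contain well-being. Section 3.6.2 defers to section 7 for the methods, section 7 names its terms, and the final covariate list could properly sit in a statistical analysis plan that is not shown. This stands in part. A reader might infer that the planned regressions already adjust for well-being, and the documents do not show that. What they show is a commitment to adjust in 3.6.2 that section 7 does not carry out. The commitment is wrong as stated, and a later plan would inherit it.

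A second reply concerns the numbers. The factor 1 − r² needs well-being to be a consequence of the same 12-month score. The protocol does not say which visit's well-being would be used. A week 6 or month 6 value cannot result from 12-month EF. It could reflect earlier EF and so lie on the path from APA status to later EF, where adjusting also removes part of the effect, but by an amount the formula does not give. The protocol also attributes reduced well-being partly to incontinence, and it does not deny that well-being may influence EF. All of this stands, so the table in the working is an illustration and not an estimate.

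Third, a reader might infer that EF would be adjusted for itself, since the named tools also measure EF. The overlap is a fair warning, but no item or domain is designated as the well-being score. The endpoint list also refers to quality-of-life questionnaires that it does not name, so the claim cannot be established.

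Fourth, this is a feasibility study, and no primary or secondary endpoint is an adjusted APA-EF association. That is correct and limits the weight of the point.

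**Conclusion.** The point holds as a wrong statement in section 3.6. Post-operative overall well-being is labelled a confounder and marked for adjustment, although it follows the exposures in time and the protocol itself describes it as affected by sexual function. Adjusting for it would bias the exploratory associations of APA status and surgical quality with EF, generally towards zero. The direction rests on the protocol's statement that sexual side effects affect well-being. The size cannot be derived from the documents: the multipliers 0.91, 0.75 and 0.51 hold only for the assumed r and the pure-consequence model.

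A reader might also infer that the future study would be sized on too small an SD. The documents do not support this. The variability endpoint is the plain mean and SD of IIEF scores at follow-up, which no regression covariate changes. Recruitment, retention and the other feasibility endpoints are likewise unaffected. This is worth correcting because the error could pass to the full-scale study and the correction is cheap, but it does not threaten what this study is mainly set up to measure.

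**What to change.** 1. In section 3.6.1, remove post-operative overall well-being from the list of confounders. In section 3.6.2, take it out of the adjustment commitment and state that it will be reported as an outcome.
2. Limit the main adjustment set to variables fixed before or at surgery: comorbidities, baseline EF, video-rated NVB-sparing quality and intraoperative complications. Restricting it to pre-surgical variables alone would go too far, because NVB-sparing quality is a surgical confounder in section 3.6.1 and a model term in section 7.
3. Label any model that contains post-operative variables, including post-surgical complications, as exploratory.
4. Align section 3.6 with section 7 so that both give the same adjustment set. Section 7 already omits well-being, but it does not name comorbidities or intraoperative complications.

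The cost is a few sentences in sections 3.6.1, 3.6.2 and 7. No visit, questionnaire, procedure or data item changes.

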3.7 Assessment of the pelvic vasculature with a postoperative an MR angiogram

By obtaining an MR angiogram with an arterial phase after the surgery, we will be able to confirm whether there is blood flow in the accessory pudendal arteries after surgery. This additional MRI at least 3 months after surgery will be only offered to patients who have an accessory pudendal artery on their preoperative mpMRI. This will be useful to assess whether the APA patency after surgery has an effect on EF outcomes. If there is an incidental finding on this MRI relating recurrence, then the parent team and the CI will be notified promptly. This will lead to further appropriate action.

We will follow an established and validated protocol for MRI angiography on month 3 (described in Appendix)

3.8 Penile doppler US (optional): Objective assessment of EF using erectile haemodynamics.

Penile Doppler ultrasound (PDUS) is a well-established diagnostic tool for ED in specialist clinical practice. As an optional part to the study, we will offer patients an opportunity to assess their erectile haemodynamics prior to surgery through a PDUS. The APA presence, features or absence will be known through review of their preoperative mpMRI. With that knowledge, the optional PDUS before surgery will outline the effect of APA on the haemodynamics in healthy men with prostate cancer.

Patients who will not respond to PDE5i after surgery will be offered with a PDUS to evaluate the flow of penile arterial blood and to provide objective evidence that the underlying cause of ED is arterial.

This will be an optional part to the study and will be offered at 6 months or earlier if patients wish to have ICI to treat their ED. This is the accepted standard of care for the evaluation of post-RARP ED that is not responding to medical treatment.

The standard penile doppler US protocol will be followed for patients who opt for this assessment. Details of the protocol are provided in appendix.

Blood tests: The metabolic assessment of ED includes testosterone, HbA1c and lipid profile biochemical profile. As part of routine post-surgical PCa follow-up all patients have a PSA tests done
EVERiST, EDGE (Sponsor) number 177704, IRAS number 335003, Protocol version 1.0, 07/10/2025

at 2 to 3 months and either 1 or 3 more until month 12 depending on cancer features. We will use these time points to obtain the blood samples required for assessment of ED. Hence, additional hospital visits will be avoided. These blood samples that will be requested are standard part of assessment of ED therefore not leading to additional NHS costs. If the metabolic ED blood panel is normal, this will not be repeated again. Any abnormalities in these will be communicated to the patient and their general practitioner and where necessary, treatment will be recommended i.e. if patients have a new diagnosis of diabetes, the patient and their general practitioner will be informed to repeat the test and start treatment if necessary. These will then be retrospectively recorded by the research team. No samples will be obtained or stored as part of this research.

Postoperative MRI: For patients that undergoing bilateral NVB sparing RARP, with an APA identified on their preoperative mpMRI, an additional MRI will be offered at least 3 months after surgery to assess whether the accessory artery was preserved or sacrificed.

Penile doppler US: For patients opting to undergo a PDUS before and after surgery, an additional hospital visit may be required prior to surgery to perform the preoperative PDUS. Postoperatively, if patients do not respond to oral medication treatment for ED, they will be offered a PDUS during the same visit as their tutorial for intracavernosal injection (ICI) therapy, minimizing the need for additional hospital visits.

This tutorial, conducted in the clinic, ensures patients are proficient in self-administering alprostadil or Invicorp to achieve an erection. This approach aligns with the current standard of care for patients unresponsive to oral medications. During the clinic session, a penile Doppler US will be performed in conjunction with ICI self-administration to assess erectile haemodynamics comprehensively.

Additional visits:

Patients who have an APA identified on their preoperative mpMRI that are undergoing a bilateral NVB sparing RARP will be offered an additional MRI angiogram at 3 months to assess the patency of the accessory artery. All other aspects of their care will be the same including the preoperative andrology consultation, recording of their intracorporeal surgery as well as post operative care.

End of study

The end of the study is defined as the date of the final 12-month follow-up visit for the last recruited participant. Recruitment will stop once between 20 and 40 patients have been enrolled, and all participants will be followed for 12 months after surgery.

Table 1: showing Study specific schedule as well as standard clinic schedule

	Study specific schedules	Standard clinical schedule	Study specific assessments	Routine clinical assessments
Preoperative mpMRI prostate		X		
Prostate Biopsy		X		
Multidisciplinary meeting		X		
Clinic appointment to discuss treatment options		X		

Clinic appointment for patient decision: for surgery		X		
Radiology preoperative MRI meeting: for NVB surgery, identify APA	X (identify APA~)	X		
Eligibility assessment by study team	X~			
Preoperative andrology telephone clinic		X	IIEF-EFD, EPIC-26	IIEF-EFD, EPIC-26
Consent for research	X			
Pre-assessment for surgery		X		Routine bloods and assessments.
Optional: Penile doppler before)			X	
Surgery: RARP		X	Consent for research	
First surgical follow up appointment 6 weeks		X		
Andrology appointment at 6 weeks, 6, 12 and 24 months.		X	IIEF-EFD, EPIC-26	
Routine cancer and surgical follow up at 3 months		X		All patients: PSA, Patients with ED: Testosterone, HbA1c, lipid profile

~ This is done by the study team and does not constitute an additional visit by the patients.

5. ELIGIBILITY CRITERIA

Eligibility criteria	
Inclusion criteria	
 Men diagnosed with cT2-T3a N0 M0 PCa aged between 18 and 79 from all ethnic backgrounds. Patients who underwent a prostate mpMRI before prostate biopsy. Medically fit to undergo RARP. Diagnostic quality prostate biopsies concordant with a diagnostic quality prostate mpMRI adequate to provide a surgical plan.

	
 • Scheduled for RARP with a recommendation of BL NVB spare based on multidisciplinary meetings informed by mpMRI, biopsy result and clinical factors. • Sexually active men with no to mild ED at baseline based on IIEF-EFD (≥ 24). • Preference to preserve erectile function for sexual intercourse. • Ability to read English sufficiently to understand PIS and able to give informed consent.
Exclusion criteria	
 • Established moderate/ severe ED (IIEF-EFD < 24) • Patients who received neo-adjuvant androgen deprivation therapy. • Patients with previous surgery for benign prostatic enlargement • Patients who received previous treatment for prostate cancer: External beam radiotherapy, brachytherapy, focal therapy, chemotherapy. • Previous pelvic or penile fracture • Previous surgery for ED • Poor quality prostate mpMRI or biparametric MRI (no contrast) • Established vascular disease (ischaemic heart disease, cerebrovascular disease, peripheral vascular disease)

5 RECRUITMENT

1. Screening for eligible will be carried out by looking through
 - a. Theatre lists for patients undergoing RARP
 - b. MDT lists
 - c. MRI planning meeting where NVB sparing plan is made
2. Enrolment for eligible patients at the pre-operative andrology telephone appointment
 - a. This is standard of care at UCLH.
 - b. Eligible patients will be presented with the research and recruited as per detailed below
 - c. PIS and consent forms
 - d. Baseline questionnaires

Currently, all patients that are scheduled for RARP at UCLH receive phone call from the andrology department clinical team to outline the expectation of EF changes and recovery after surgery. This is currently standard operative procedure at UCLH and is routine provide patient centred andrology care. During this telephone consultation, all eligible patients will be given information about the research. If they are interested to learn more about this, the patient information sheet as well as research consent form will be emailed or posted to the patient. This will be at least 24 hours prior to their surgery. A dedicated member of the clinical research team will approach them again during their hospital admission and provide them with the chance to ask any questions. If patients wish to take part in the study, the consent form will be collected from the patient by the andrology research team during their hospital admission.

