Primary end-points	
 1. Recruitment and Retention Rates 
 a) Percentage of patients who satisfy the eligibility criteria amongst patients who opted for RARP b) Percentage of patients consenting to participate (denominator= number of eligible patients approached) c) Percentage of participants completing the study (denominator=number of patients consenting for the study) 2. MRI Assessment Feasibility 
 -Time required for APA mapping on mpMRI 3. Intraoperative Video Analysis

	
 -Percentage of RARP procedures with complete, analysable video recordings (denominator= number of patients consenting for the study) -Time required for video analysis of APA preservation 4. Erectile Function Questionnaire Completion 
 -Completion rates of validated EF questionnaires such as the International Index of Erectile Function (IIEF) questionnaire & EPIC -26 sexual domain within patients consenting to join the study. -Time taken to complete the questionnaires 5. Post-operative MRI assessment feasibility 
 -Proportion of patients who accepted to have a 3-month follow-up MRI angiogram within patients consenting to join the study -Proportion of patients who have a patent APA 6. Baseline Penile Doppler US (PDUS) assessment feasibility 
 -Proportion of patients accepting to have a preoperative PDUS. -Proportion of patients who received a baseline Doppler scan. 7. Postoperative PDUS assessment feasibility 
 -Proportion of patients who accepted to have a postoperative PDUS -Proportion of patients who received a postoperative PDUS

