6 CONSENT

Potential participants will be approached via telephone during their planned preoperative andrology telephone appointment prior to their surgery date. They will receive an electronic PIS sent via NHS email or post. They will have at least 24 hours to read the study, reflect on the information provided and have the opportunity to ask questions. During their hospital hospitalisation, a selected member of the clinical team will approach them again and provide them with the opportunity to ask any questions and sign the consent form for those agreeing to enrol in the study.

Patients may express interest by phone, but formal consent will only be obtained in writing after discussion with the research team.. The electronic consent platform will be developed within the RedCAP service hosted behind the UCL Data Safe Haven, which conforms to NHS Data Security & Protection Toolkit, General Data Protection Regulation, and ISO 27001 Information Security. Patients cannot sign consent until a face-to-face (or secure e-consent) discussion with the research team.

A copy of the consent form will be given to the patient, a copy uploaded to the electronic health records of the patient and the original will be stored in the ISF. All members of the team consenting patients will be suitably qualified, experienced, and will have been delegated this duty by the CI/ PI on the Staff Signature and Delegation of Tasks.

When the participant receives the participant information sheet (PIS), it will be recorded in the patient's medical notes (or electronic health record). The PIS and consent form will be reviewed and updated, if necessary, throughout the study (e.g. where new safety information becomes available) and participants will be re-consented as appropriate.

At every review at regular intervals, patients will be given the opportunity to withdraw from the research study.

Electronic Consenting

The electronic consent platform will be developed within the RedCAP service hosted behind the UCL Data Safe Haven, which conforms to NHS Data Security & Protection Toolkit, General Data Protection Regulation, and ISO 27001 Information Security.

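### The protocol gives conflicting time points for study consent, so a preoperative penile Doppler could come before consent and make part of primary endpoint 6 ambiguous

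*Protocol*

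**What the plan says.** **Signature at admission.** Section 5 (Recruitment) describes a preoperative telephone call, then the information sheet and consent form sent by email or post at least 24 hours before surgery. After that, "the consent form will be collected from the patient by the andrology research team during their hospital admission". Section 6 (Consent) follows the same sequence: "During their hospital hospitalisation, a selected member of the clinical team will approach them again" to "provide them with the opportunity to ask any questions and sign the consent form for those agreeing to enrol in the study". It rules out the call itself as consent: "Patients may express interest by phone, but formal consent will only be obtained in writing after discussion with the research team".

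**Earlier consent.** Item 2 of section 5 puts enrolment, with the consent forms, at the telephone appointment. Table 1 in section 4 has a row "Consent for research" above both the pre-assessment row and the optional preoperative Doppler row. The same entry then appears again in the row for surgery. Section 6 also permits an electronic route, without saying when: "Patients cannot sign consent until a face-to-face (or secure e-consent) discussion with the research team".

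**The scan.** Section 4 says of the optional preoperative PDUS that "an additional hospital visit may be required prior to surgery to perform the preoperative PDUS". Table 1 marks it as a study-specific assessment.

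**What depends on it.** Primary endpoint 6 has two parts: the proportion accepting a preoperative PDUS, and "Proportion of patients who received a baseline Doppler scan". Neither states a denominator. The log in section 3.1 counts men who both consent to and undergo a baseline PDUS. Under Assessments of Adverse Events (within section 11.1), events are assessed from consent to 90 days after surgery.

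**The concern.** The preoperative PDUS is the one study-specific test on the patient before surgery. It requires an intracavernosal injection in men who enter with IIEF-EFD of at least 24. Section 11 gives the risk of a prolonged painful erection as 1% with alprostadil and 0.3% with Invicorp. The protocol should therefore leave no doubt that study consent comes first, but its only two narrative accounts of signing place the signature at the admission.

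Two things are at stake. One is participant protection and safety recording: a complication of a scan done before signature would arise before the adverse event window opens. The other is measurement: the receipt part of a primary feasibility endpoint would depend on which section the team followed. A low figure could then be read as poor acceptability when it partly reflects the timing of the form.

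**Working it through.** No arithmetic in the protocol bears on this point, and no stated figure needs reproducing. The check is the order of events.

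**Order A: the narrative in sections 5 and 6**
1. Telephone appointment: study introduced, interest recorded, no consent.
2. Information sheet and form sent, no later than 24 hours before surgery.
3. Optional PDUS, possibly at an extra visit before surgery (section 4). Section 11 has patients monitored for at least 2 hours before going home, which fits an outpatient visit better than a scan during the surgical admission.
4. Hospital admission: form signed.
5. Surgery.

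**Order B: Table 1, first consent entry**
1. Telephone appointment.
2. Consent for research.
3. Pre-assessment.
4. Optional PDUS.
5. Surgery (where the consent entry appears a second time).

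The two orders differ in whether consent comes before or after the PDUS. The second entry in Table 1 agrees with order A, so the table carries both orders within itself.

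**Consequence for endpoint 6, receipt part.** Let n be the number of consented men (20 to 40 by the target) and k the number scanned at a visit before admission.
- Order A, only scans after study consent count: 0/n, whatever k is.
- Order A, all scans count: k/n, with all k done before enrolment.
- Order B, or e-consent before the PDUS visit: k/n, with all k done after consent.

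The protocol does not say which count applies. Endpoints 1b and 1c, and the relevant items of endpoints 3, 4 and 5, name the men they are taken over; endpoint 6 does not.

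**Consequence for endpoint 6, acceptance part.** Willingness can be noted at the telephone call, so this part need not be zero under either order.

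**Consequence for safety recording.** The assessment window runs from consent to 90 days after surgery. Under order A, a scan at step 3 precedes the start of the window at step 4. Under order B it falls inside. Section 11.3 would still have any event written in the medical records, so it would not go wholly unrecorded. It would fall outside the stated period for assessing severity, causality, seriousness and expectedness.

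**The case against.** A reader might infer that endpoint 6 must be either zero or built entirely on scans before consent. The text does not force that. Table 1 has a consent row ahead of the Doppler row, section 5 also lists enrolment at the telephone appointment, section 4 names the surgeon's preoperative consultation as a second point of approach, and e-consent is allowed with no time attached. Section 4 says only that an extra visit may be needed. On several routes, signed consent can come first.

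A reader might also call a scan before study consent an ethics breach. The protocol prescribes no scan without written consent. Section 11 has patients consented again for the PDUS, and the PDUS protocol in the appendix opens with verbal and written consent. The word again suggests that study consent was meant to come earlier. This stands as evidence of intent. It does not supply the missing time point, and consent to the procedure does not replace consent to the study.

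Two further inferences fail. The baseline questionnaires come before the signature, but Table 1 also lists them as routine care, and the IIEF-EFD score is needed to establish eligibility. Losses between telephone interest and signature do not make the consent rate (endpoint 1b) wrong: the protocol gives no rate for such losses, and they are part of what a feasibility consent rate should show.

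It is also fair to say that the PDUS is optional and that endpoint 6 is one of seven groups of primary endpoints. That limits the reach of the problem. The contradiction itself remains.

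**Conclusion.** The point holds as an internal contradiction on when study consent is taken. Sections 5 and 6 put the signature at admission; item 2 of section 5 and the first consent row of Table 1 put it earlier; the surgery row of Table 1 puts it late again.

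Its effect depends on two assumptions: that the narrative in sections 5 and 6 is what staff follow, and that the PDUS is done at a visit before the admission. If both hold, a study-specific injection test precedes study consent and the start of the adverse event window, and the receipt part of endpoint 6 is either 0/n or a count of scans done before enrolment, for any n from 20 to 40. If either fails, the endpoint can be measured normally. The acceptance part of endpoint 6 is not affected in the same way. The matter should be settled before recruitment starts, because it concerns consent before an invasive study procedure and costs little to correct.

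**What to change.** 1. Reconcile section 4 (including Table 1), section 5 (Recruitment) and section 6 (Consent) on one sequence: telephone appointment, at least 24 hours to read the information, discussion with the research team, written or secure e-consent, and only then any study-specific PDUS. Keep signing at admission as a stated fallback.
2. Delete the consent entry from the surgery row of Table 1.
3. For endpoint 6, state that the denominator is consented men. Report separately those who consented only at admission and so could not have the scan after consent. Men who were offered the scan, for example by telephone, and declined it stay classed as decliners whenever they signed. Classing everyone who signed at admission as not offered would misclassify them.

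The cost is wording in three sections, one table entry and the endpoint definition. The RedCap e-consent platform is already planned. The research team's consent discussion moves earlier for men who would otherwise have signed at admission.
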